Study Design:	
This phase II, randomized, placebo-controlled, double-blind, efficacy study is designed to evaluate HB-adMSCs for the treatment of Coronavirus Disease (COVID-19).
 
The screening period, up to 7 days long for each patient, will be used to assess eligibility. Once eligibility is confirmed, the patient will be considered enrolled.
 
Upon study completion, the investigators should know whether or not HB-adMSCs are effective to treat patients with Coronavirus Disease.
 
To ensure that the drug is safe, a Medical Monitor and Data Safety Monitoring Board (DSMB) will oversee the entire study,

	review any clinically significant laboratory data, including complete blood counts, serum chemistry, imaging studies, EKGs and adverse events., serum chemistry and adverse events will be reviewed.
Selection of Patients:	
Inclusion Criteria:
 
 1. Men, and women, over 18 years of age inclusively. 2. Patient is suspected to have COVID-19 infection 3. Provides consent or consent is given by their legally authorized representative (LAR) 4. Agrees to the collection of venous blood per protocol. 
Exclusion Criteria:
 
 1. Pregnancy, lactation and those who are not pregnant but do not take effective contraceptive measures, in women of childbearing age. Absence of pregnancy will be confirmed through urine pregnancy test. 2. Patients who have participated or are participating in a clinical trial of an experimental vaccine for SARS-CoV-2 or coronavirus during the study or within 30 days. 3. Inability to provide informed consent or to comply with test requirements. 4. Any medical disease or condition that, in the opinion of the site Principal Investigator or sub-investigator, precludes study participation. Including acute, subacute, intermittent or chronic medical disease or condition that would place the subject at an unacceptable risk of injury, render the subject unable to meet the requirements of the protocol, or may interfere with the evaluation of responses or the subject's successful completion of this trial.
Planned Sample Size:	Population: 100 patients. The sample size required assumes a 15% drop-out of patients.

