
The drug for this submission is Hope Biosciences' allogeneic, adipose-derived culture-expanded mesenchymal stem cells (HB-adMSCs) to treat COVID-19. We hypothesize that the immunomodulatory properties of MSCs will inhibit cell-mediated immune inflammatory responses and MSC endogenous regenerative properties will reduce pathological changes of lung associated with COVID-19. The population we are proposing to treat are suspected to be positive

for COVID-19, which will be confirmed by testing during the trial. We have preclinical safety and efficacy data, as well as clinical evidence of the safety of HB-adMSCs in patients in ongoing phase I/IIa clinical trials for Rheumatoid Arthritis (NCT03691909), Traumatic Brain Injury and/or Hypoxic-Ischemic Encephalopathy (NCT04063215), and Alzheimer's Disease (NCT04228666), as well as individual expanded access for Parkinson's Disease (NCT04064983), Spinal Cord Injury (NCT04064957 and NCT03925649), and Cerebral Palsy (NCT04029896). We have experience with an individual expanded access for Pancreatic Cancer (NCT04087889) who received allogeneic HB-adMSCs, as well. All treatments have been well-tolerated, with no severe adverse events related to the study drug.

Study Objectives and Endpoints

Study Objectives

Primary:

- To investigate the safety and efficacy of HB-adMSCs as a treatment for patients suspected to have COVID-19.

Secondary:

- To investigate the safety and efficacy of HB-adMSCs in improving clinical status of patients suspected to have COVID-19 infection.

Study Endpoints

Primary:

- change from baseline in inflammatory markers (TNF-alpha, IL-10, IL-6, C-Reactive protein)
- change from baseline oxygenation
- Time to return to room air (RTRA)

Secondary:

- Change in clinical laboratories
- Change from baseline Chest X-ray
- Change from baseline CT scan
- Change from baseline in exploratory markers (D-dimer, myoglobin, troponin, creatinine kinase, serum ferritin, CD3CD56, CD4/CD8, VEGF)
- Time to negative PCR test results
- Change from baseline in the 7-point ordinal scale
- Cumulative incidence of serious adverse events (SAEs) or adverse events (AEs)

Investigational Plan

This Phase II, randomized, placebo-controlled, double-blinded, trial assesses efficacy in a population of hospitalized patients to evaluate efficacy of HB-adMSCs to treat Coronavirus Disease. It is designed to be conducted in 2 arms:

Consenting patients will be randomly assigned to one of two arms:

Arm 1 (HB-adMSCs) (n=60)

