Patients will receive four intravenous infusions of 100 million HB-adMSCs throughout the entire duration of the study.

Arm 2 (placebo) (n=40)

Patients will receive four intravenous infusions of placebo (saline solution) throughout the entire duration of the study.

Safety assessments will be ongoing. Safety tests will include EKG, Complete Blood Count with differential, Complete Metabolic Profile (to include renal function and hepatic function) and Coagulation Panel screening for hepatotoxicity, cytopenias, renal failure or alterations in the coagulation cascade that might entail a safety concern for the individual. Efficacy will be measured by change from baseline in inflammatory markers (IL-6, CRP, IL-10, TNF-alpha), change from baseline in oxygenation, and time to receive negative PCR test result, change from baseline in exploratory markers (D-dimer, myoglobin, troponin, creatinine kinase, serum ferritin, CD3CD56, CD4/CD8, VEGF), time to return to room air (RTRA), change from baseline chest x-ray, change from baseline CT scan, and change from baseline in 7-point ordinal scale.

Selection and Withdrawal of Patients

Inclusion Criteria

1. Men, and women, over 18 years of age inclusively.
2. Suspected COVID-19 infection
3. Provides consent or consent is given by their legally authorized representative (LAR)
4. Agrees to the collection of venous blood per protocol.

Exclusion Criteria:

1. Pregnancy, lactation and those who are not pregnant but do not take effective contraceptive measures, in women of childbearing age.
2. Patients who have participated or are participating in a clinical trial of an experimental vaccine for SARS-CoV-2 or coronavirus during the study or within 30 days.
3. Inability to provide informed consent or to comply with test requirements.

4. Any medical disease or condition that, in the opinion of the site Principal Investigator or sub-investigator, precludes study participation. Including acute, subacute, intermittent or chronic medical disease or condition that would place the subject at an unacceptable risk of injury, render the subject unable to meet the requirements of the protocol, or may interfere with the evaluation of responses or the subject's successful completion of this trial.

Withdrawal, Removal, and Replacement of Patients

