If a patient is screened and fails to meet any study entry criteria or falls outside the screening window, they may be re-screened only once. Such patient must be fully consented a second time before the second set of screening assessments take place and shall be assigned a new subject number. Investigator discretion should be exercised in determining who may be re-screened.

In case of doubt about the accuracy of screening laboratory value(s), the laboratory test(s) may be repeated provided that this can be done within the 7-day screening period without the need to repeat all other screening procedures (i.e., no re-screening).

If a patient is enrolled after they have been re-screened, such subject shall be assigned a new subject ID number, different from the previous attempt to enroll.

Assessments by Week

Assessments will occur as outlined in the following subsections. For visits at Day 0 through 28 days, there will be a window of ± 3 days.

Screening

The Screening visit will last up to 7 days. Results from laboratory samples collected in this visit will set a baseline. These are the procedures to be performed during this visit:

- Written Informed Consent will be obtained from the subject or their legally authorized representative (LAR).
- COVID-19 confirmatory test results may be in progress during the screening period.
- Demographic Information will be obtained.
- Medical History and Current conditions will be obtained,
- Concomitant Medications will be obtained. Every medication listed should match a condition in the medical history.
- Vital signs will be obtained.
- Weight and Height will be measured.
- A physical exam will be performed.
- Blood and urine samples will be collected for laboratory assessments (CBC with differential, chemistry, and coagulation, pregnancy if appropriate).
- Ascertain patient eligibility by evaluating patient results against the inclusion/exclusion criteria.

Upon completion of all Screening procedures, the Principal Investigator must confirm and document the patient eligibility in the “Screening Result” CRF.

Infusion #1 - Day 0 (Baseline)

- Weight will be measured
- Vital Signs will be measured.
- Concomitant medications will be reviewed and updated if necessary.

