- Medical History will be reviewed and updated if necessary. This includes recording results of COVID-19 testing. If the patient reported a medication which does not match the current medical history, further investigation will be required to determine whether it was an Adverse Event, or the patient just forgot to mention it before. If it is found to be an AE, it should be recorded in the appropriate CRF. If the patient forgot to mention it before, a note to file (NTF) should be made to clarify the case.
- A PCR analysis to detect SARS-CoV-2 virus will be performed with a nasal swab
- Blood samples will be collected for laboratory assessments.
- Ordinal Scale to be performed.
- Administer investigational product.
- Monitor for AEs. Observe the patient for at least 1 hour after infusion for symptoms of infusion-related reactions and allergic reactions, including anaphylaxis (See Appendix 1).
- Instruct the patient on recognition of delayed serious allergic reactions, including anaphylaxis and seeking for medical assistance.
- Chest X-ray will be performed or collected from hospitalization due to COVID-19.
- CT scan will be performed or collected from hospitalization due to COVID-19.

Infusion # 2 (Day 3) and #3 (Day 7) and #4 (Day 10)

- Weight will be measured
- Vital Signs will be measured.
- Concomitant medications will be reviewed and updated if necessary.
- Medical History will be reviewed and updated if necessary. This includes recording results of COVID-19 testing. If the patient reported a medication which does not match the current medical history, further investigation will be required to determine whether it was an Adverse Event, or the patient just forgot to mention it before. If it is found to be an AE, it should be recorded in the appropriate CRF. If the patient forgot to mention it before, a note to file (NTF) should be made to clarify the case.
- A PCR analysis to detect SARS-CoV-2 virus will be performed with a nasal swab
- Blood samples will be collected for laboratory assessments.
- Ordinal Scale to be performed.
- Administer investigational product.
- Monitor for AEs. Observe the patient for at least 1 hour after infusion for symptoms of infusion-related reactions and allergic reactions, including anaphylaxis (See Appendix 1).
- Instruct the patient on recognition of delayed serious allergic reactions, including anaphylaxis and seeking for medical assistance.

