## 2. SUMMARY OF KEY PROTOCOL INFORMATION

### 2.1. Study Objective(s) and Endpoint(s)

Objectives	Endpoints
Primary Objective	Primary Endpoint

To investigate the safety and efficacy of HB-adMSCs in the treatment of patients with COVID-19 by decreasing inflammation, improving oxygenation, and decreasing time to return to room air (RTRA)

	

Change from baseline in inflammatory markers (TNF-alpha, IL-10, IL-6, C-Reactive protein)

Change from baseline oxygenation

Time to return to room air (RTRA) and proportion of patients with room air status

Secondary Objectives	Secondary Endpoints

Objectives	Endpoints

• To investigate the safety and efficacy of HB-adMSCs in improving clinical status of patients suspected to have COVID-19).

	

• Change in clinical laboratories

• Change from baseline Chest X-ray

• Change from baseline CT scan

• Change from baseline in exploratory markers (D-dimer, myoglobin, troponin, creatinine kinase, serum ferritin, CD3CD56, CD4/CD8, VEGF)

• Time to negative PCR test results

• Change from baseline in the 7-point ordinal scale

• Cumulative incidence of serious adverse events (SAEs) or adverse events (AEs)

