### **5.3.2 Examination of subgroups**

Secondary analyses will evaluate heterogeneity of treatment effect as a function of gender, age, ethnicity and strata defined by pre-existing condition and illness severity. The approach to subgroup analyses will utilize skeptical, informative priors to increase the likelihood of future replication.

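### The documents disagree on whether the target is confirmed or suspected COVID-19, and no planned analysis of a primary endpoint or the ordinal score isolates patients who were PCR-positive before the first infusion

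*Protocol*

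**What the plan says.** **Entry.** The Synopsis (Selection of Patients) asks for "Patient is suspected to have COVID-19 infection", and the body's Inclusion Criteria for "Suspected COVID-19 infection". Neither asks for a positive test. Background and Study Rationale describes the population as suspected positive "for COVID-19, which will be confirmed by testing during the trial". The Screening section adds: "COVID-19 confirmatory test results may be in progress during the screening period". Table 2 places eligibility and randomization at Screening.

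**Testing.** The Day 0 procedures include "A PCR analysis to detect SARS-CoV-2 virus will be performed with a nasal swab", listed ahead of product administration. COVID-19 test results are recorded in the CRF as medical history (Prior and concomitant conditions).

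**Target population.** The SAP 2.1 primary objective, matching the Synopsis, is "To investigate the safety and efficacy of HB-adMSCs in the treatment of patients with COVID-19 by decreasing inflammation". The Synopsis (Study Design) states the expected conclusion: "Upon study completion, the investigators should know whether or not HB-adMSCs are effective to treat patients with Coronavirus Disease". By contrast, the primary objective in the protocol body, the protocol and SAP hypotheses, and the analysis question in SAP 5.7 all name suspected disease.

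**Analysis.** The efficacy set is defined only by receipt of all four infusions (Protocol, Analysis Population; SAP 4). The covariates are baseline and the stratification variables: site, severity, pre-existing condition, ethnicity and age group (SAP 5.4.1). The subgroup section covers "heterogeneity of treatment effect as a function of gender, age, ethnicity and strata defined by pre-existing condition and illness severity". The protocol's additional sub-analysis is by use of other experimental COVID-19 treatment.

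**The concern.** A trial may legitimately treat on suspicion and analyse everyone it treated. The difficulty is that these documents promise an answer for two populations and plan an analysis for only one of them.

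Suppose some enrolled patients have another illness and respond less to the cells. The all-patient estimate then mixes two effects and understates the effect in COVID-19. A weak result could not be attributed either to the product or to the case mix. If a confirmed-case analysis is added after the data are seen, it will be post hoc, although the swab it needs is already scheduled.

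**Working it through.** **1. Where infection status enters the plan**

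| Place | Uses pre-infusion PCR? |
|---|---|
| Efficacy set (Protocol, Analysis Population; SAP 4) | No |
| Stratification and covariates (SAP 5.4.1) | No |
| Subgroups (SAP 5.3.2) | No |
| Protocol sub-analysis | No; split by other experimental treatment |
| Primary model (SAP 7.1.4.2) | No |
| Ordinal-scale model (SAP 7.2.4.2) | No |
| Confounder rule (SAP 5.1, 7.1.4.1) | Only if the arms differ on it and it correlates with outcome |
| Time to negative PCR | Implicitly: clearance presupposes an earlier positive |

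The last two rows do not fill the gap. The confounder rule adjusts an average effect and would not fire if infection status were balanced. The PCR endpoint says nothing about inflammatory markers, oxygenation, room air or the ordinal score.

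**2. What mixing does to the effect**

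Let Δ be the effect in infected patients, p the uninfected share, and kΔ the effect in the uninfected. The all-patient effect is

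(1−p)Δ + p·kΔ = Δ[1 − p(1−k)].

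- With k = 0: 0.90Δ, 0.80Δ and 0.70Δ at p = 10%, 20% and 30%.
- With k = 0.5: 0.95Δ, 0.90Δ and 0.85Δ.
- With k = 1: no change at any p.

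**3. Whether restriction gains power**

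The plan has no power figure to reproduce; the protocol bases its sample size on expected demand. As a yardstick only, take the planned 60 v 40, a two-sided 5% t-test (the level SAP 2.4 sets for supplementary frequentist analyses) and an assumed standardised effect of 0.6 in infected patients. The all-patient columns use 60/40 with effect 0.6[1 − p(1−k)]. The confirmed-only columns use effect 0.6 with both arms multiplied by (1−p)s, where s is swab sensitivity and false positives are ignored.

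| p | All patients, k = 0 | All patients, k = 0.5 | Confirmed, s = 1 | Confirmed, s = 0.8 |
|---|---|---|---|---|
| 0% | 82.9% | 82.9% | 82.9% | 73.8% |
| 10% | 74.5% | 79.0% | 78.8% | 69.1% |
| 20% | 64.4% | 74.5% | 73.8% | 63.9% |
| 30% | 53.1% | 69.6% | 67.9% | 57.9% |

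The pattern follows from the noncentrality. Restriction wins when √[(1−p)s] exceeds 1 − p(1−k).

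- With k = 0 this reduces to s > 1−p, so at s = 0.8 the two analyses tie at p = 20%.
- With k = 0.5 and a perfect swab, (1 − p/2)² = 1 − p + p²/4, which is larger than 1 − p, so restriction never wins.

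These powers are optimistic about numbers. With 15% drop-out the arms are 51/34, and the p = 0 figure is 76.4%.

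**The case against.** The strongest reply is that the trial's question is about suspected patients. The body objective, both hypothesis sections and SAP 5.7 say so, and for that population the all-patient analysis is the right one and nothing is diluted. This stands as far as it goes. It shows that the all-patient analysis belongs in the plan. It does not remove the conflict with the Synopsis, SAP 2.1 and the stated conclusion.

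A reader might infer three stronger things that the documents do not support.

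- *Uninfected patients certainly weaken the result.* No uninfected share is given. The patients are described as hospitalised, so the share may be small. The proposed mechanism is general immunomodulation, so some effect in the uninfected cannot be excluded.
- *A confirmed-only analysis would be more powerful.* The table shows that this depends on k and s, neither of which is in the documents. The primary inference is also Bayesian, so these powers describe no planned decision.
- *No efficacy analysis depends on PCR.* Time to negative PCR does, through its clearance rule, although the SAP does not say how patients negative at Day 0 are handled.

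It might also be objected that restricting on PCR breaks the randomised comparison. It does not in itself: the sample precedes the first infusion in a double-blind trial, so treatment cannot have altered it.

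**Conclusion.** The point holds as a cheap improvement. Two things are established from the text. The target population is unreconciled, and no planned analysis estimates the effect on any primary endpoint or the ordinal score in patients confirmed before treatment.

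The consequence is conditional. If uninfected patients were enrolled and respond less, the all-patient effect falls short of the effect in COVID-19 by the fraction p(1−k). That is 10% to 30% for p between 10% and 30% with no response in the uninfected, half that if they get half the effect, and nothing if they respond equally. The values of p, k, swab sensitivity and the 0.6 effect are assumptions.

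The case for acting rests on interpretability and pre-specification. It does not rest on a gain in power, which is not guaranteed.

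**What to change.** - State one target population, and align the Synopsis, the protocol body, SAP 2.1, 2.4 and 5.7, and the stated conclusion with it.
- Add to SAP 4 and 7 a pre-specified analysis of the primary and secondary efficacy endpoints, by randomised arm, in patients with a positive SARS-CoV-2 PCR on a sample taken no later than the Day 0 pre-infusion swab. Report it beside the analysis of all suspected patients.
- Add baseline PCR status to the SAP 5.3.2 subgroups.
- Report PCR-negative and missing counts by arm, with a stated rule for missing swabs.
- Base any statement about patients with COVID-19 on the confirmed analysis.

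Re-applying the suspicion criterion at Day 0 is not recommended. Table 2 puts randomization at Screening, so it could remove patients after randomisation.

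**Cost.** SAP wording, protocol alignment and one further run of each model. No new data are needed, because the Day 0 PCR is already scheduled. The SAP is marked Draft, and its final analysis follows database lock. The downsides are a smaller sample and the loss of infected patients with a false-negative swab. At an assumed 80% sensitivity that loss can cancel any gain, which is why the all-patient analysis must stay alongside. Accepting any positive up to Day 0, rather than the Day 0 swab alone, limits it.

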Patients will be considered to have completed the study if they complete treatment and assessments through day 28. A patient's investigational treatment should be discontinued if any of the following situations occurs:

- The Investigator believes that for safety reasons, it is in the best interest of the patient to stop treatment.
- The patient is non-compliant with the study visit schedule or other protocol requirements.
- The patient develops a severe allergic reaction that occurs following investigational product administration.

A patient may voluntarily withdraw or be withdrawn from the study at any time for reasons including, but not limited to, the following:

- Patient withdrawal of consent: At any time, a patient's participation in the study may terminate at his/her request. The specific reason for patient withdrawal will be noted on the case report form (CRF).
- Lost to follow-up: The patient stops coming for visits, and study personnel is unable to contact the patient after repeated attempts (e.g., mail, or email).
- This study may be terminated at the discretion of the Sponsor or any regulatory agency.

If a patient's infusions are discontinued at any point during the trial and the patient maintains consent to contribute additional outcome information, the patient should continue to be followed through day 28 for all safety and efficacy assessments. Investigators will be trained about the importance of retention and steps to prevent missing data. The date and reason for withdrawal are to be documented in the CRF. The study site(s) must immediately notify the medical monitor. The patients who withdraw prematurely must attend an early discontinuation visit if possible, at which time they will complete all assessments described in Table 2 under day 28. Unless the patient declines (consent withdrawn), the follow up phone call at day 28 should be done in all patients who were enrolled in the study regardless of their enrollment status.

In the event that a patient discontinues prematurely from the study due to an Adverse Event (AE) or serious AE, the event will be followed until it resolves (returns to normal or baseline values) or stabilizes, or until it is judged by the Investigator to be no longer clinically significant. Once a patient is withdrawn from the study, the patient may not re-enter the study.

Treatments

Details of the investigational product

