All medications, including over-the-counter treatments and preventative vaccines taken by the patient during the study, including those treatments initiated prior to the start of the study, must be recorded in the CRF. The entry must include the dose, regimen, route, indication, and dates of use.

Study Procedures

Table 2 outlines the timing of procedures, and assessments to be performed throughout the study.

Table 2. Schedule of Assessments

Visit Number	1	2	3	4	5	6
Days	N/A	Day 0	Day 3	Day 7	Day 10	Day 28
Visit Name	Screening	Baseline/ Infusion 1	Infusion 2	Infusion 3	Infusion 4	End of Study / Telephone Encounter**
Window Period	Up to 7 days	±3 days	±3 days	±3 days	±3 days	±3 days
STUDY PROCEDURES						
Informed Consent	X					
Demographics	X					
Inclusion and Exclusion Criteria	X					
Medical History Review	X	X	X	X	X	X
Concomitant Medication Review	X	X	X	X	X	X
Eligibility	X					
Randomization	X					
Adverse Event Monitoring		X	X	X	X	X
ASSESSMENTS						
Vital Signs	X	X	X	X	X	
Weight and Height ¹	X	X	X	X	X	
Physical Examination	X	X	X	X	X	
Ordinal Scale		X	X	X	X	X
CBC with differential	X	X	X	X	X	
Comprehensive Metabolic Panel	X	X	X	X	X	
Coagulation Panel	X	X	X	X	X	
Urinalysis with pregnancy test (childbearing age women only)	X					
PCR test for SARS-CoV-2		X	X	X	X	
Exploratory Laboratory Assessments ²		X	X	X	X	
Inflammatory Marker Laboratory Assessments ³		X	X	X	X	
EKG		X*	X*	X*	X*	
CT Scan		X				X
Chest X Ray (PA, Single View) ⁴		X				X
ADMINISTRATION						
Allogeneic HB-adMSCs Administration		X	X	X	X	

1. Height will only be measured at screening

2. Exploratory laboratory Assessments: Natural Killer Cell Surface Antigen (CD3-CD56+ Marker Analysis), Troponin, Myoglobin, Creatine Kinase (CK) MB, Serum ferritin, CD4+/CD8+ ratio, D-dimer

3. Inflammatory Marker Laboratory assessments: CRP, IL-6, IL-10, TNFa

4. Chest Xray and CT scan will be performed as scheduled, however, if the patient is discharged prior to the scheduled tests at 28 days, any imaging (CT/Xray) done at discharge

* Subsequent EKG will be performed if necessary, such as abnormal result at baseline

** Telephone encounter is conducted if subject has been discharged

Informed Consent (ICF)

Prior to commencement of any trial related activity, the investigator or designated staff will obtain written informed consent from the patient or their Legally Authorized Representative (LAR).

Patient Re-Screening

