Vital signs (body temperature, pulse, oxygen saturation, systolic and diastolic blood pressure measurements) will be evaluated at the visits indicated in the schedule of assessments. It is important that all vital signs be measured after the patient has been resting in a sitting position for at least 5 minutes. Blood pressure measurements are to be taken in the same arm for the duration of the study. Body weight (without coats and shoes) will be recorded whenever vital signs are recorded, and height (without shoes) will be recorded at screening only.

Vital sign measurements will be repeated if clinically significant or machine/equipment errors occur. Out-of-range blood pressure and pulse measurements will be repeated at the Investigator's discretion. Any confirmed, clinically significant vital sign measurements will be recorded as AEs and followed up as such.

Physical Examination

A complete physical examination (head, eyes, ears, nose, throat, heart, lungs, abdomen, skin, cervical and axillary lymph nodes, neurological, and musculoskeletal systems) will be performed at screening. In addition, medical history (including smoking history) will be recorded at screening.

A limited physical examination to verify continued patient eligibility and to follow up any change in medical history will be performed at the visits indicated in the schedule of

assessments. Symptom-driven physical examinations will be performed as clinically indicated at any study visit. All changes not present at baseline or described in the past medical history and identified as clinically noteworthy will be recorded as AEs.

Electrocardiogram

A 12-lead resting EKG will be obtained at screening and at the early discontinuation visit, if applicable. At screening, the Investigator will examine the EKG traces for signs of cardiac disease that could exclude the patient from the study. An assessment of normal or abnormal will be recorded and if the EKG is considered abnormal, the abnormality will be documented in the CRF. EKGs will be repeated if clinically significant abnormalities are observed or artifacts are present.

Clinical Laboratory Parameters

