#### **7.1.4.2. Data Analytic Models**

All primary endpoint efficacy measurements available at post-baseline at scheduled measurements (Visits 2 through 5 [infusions 1 through 4] for inflammatory markers, oxygenation, and room air status) will be analysed in a generalized linear mixed model. The model will predict each outcome as a function of the interaction between the fixed factors treatment group and time, controlling for lower order effects of time and treatment group. Models will control for stratification variables (see [Covariates and Other Strata](#)), and subject will be included as random effects.

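### The early discontinuation visit follows the Day 28 column of Table 2, which schedules no laboratory tests, vital signs or EKG and conflicts with the protocol's own safety text

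*Protocol*

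**What the plan says.** The protocol section on withdrawal, removal and replacement distinguishes two groups. Patients who only stop infusions and keep consent stay on schedule: "the patient should continue to be followed through day 28 for all safety and efficacy assessments". Patients who leave the study are to attend an early discontinuation visit where possible, "at which time they will complete all assessments described in Table 2 under day 28".

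The Day 28 column is the end-of-study column, and its footnote reads "Telephone encounter is conducted if subject has been discharged". The matching narrative (Follow Up Day 28) lists a phone call and an ordinal scale scored from that call.

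The four primary markers are defined in Table 2, footnote 3 ("Inflammatory Marker Laboratory assessments: CRP, IL-6, IL-10, TNFa"), and are marked at Days 0, 3, 7 and 10 only. Saturation is part of the vital signs: "Vital signs (body temperature, pulse, oxygen saturation, systolic and diastolic blood pressure measurements) will be evaluated at the visits indicated in the schedule of assessments". That row is also blank at Day 28.

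Three parts of the protocol point the other way. The Electrocardiogram section requires a 12-lead tracing "at screening and at the early discontinuation visit, if applicable". The Respiratory Risks text has saturation checked at every infusion visit and every follow-up visit. The Hepatic Risks and Coagulation Cascade texts place a metabolic panel and a coagulation panel at follow-up visits.

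On the analysis side, SAP section 4 puts everyone with at least one infusion in the safety set, but only those with all four in the efficacy set. SAP 7.1.4.2 models the primary endpoints at "Visits 2 through 5 [infusions 1 through 4] for inflammatory markers, oxygenation, and room air status".

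**The concern.** A discontinuation visit exists to record a patient's state on leaving. Here its content is borrowed from a visit that can be done by telephone, so an in-person exit visit yields no blood sample and no vital signs unless the investigator adds them.

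Safety is affected first. SAP 8.2 and 8.3 summarise laboratory values and vital signs in the safety set, which includes early leavers. The Hepatic Risks text also classes a defined AST/ALT rise within 72 hours of an infusion as infusion-related. An exit visit inside that window has no metabolic panel under Table 2, so it could not show such a rise.

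Efficacy is affected second. The inflammatory markers and oxygenation are primary endpoints, and SAP 7.1.4.1 promises joint modelling of missing data, sensitivity analyses and pattern-mixture models. For a patient who leaves before the Day 10 visit, those methods would have only values from infusion visits already attended. An exit sample that was never drawn cannot be recovered later.

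**Working it through.** The plan gives no figure to reproduce. The check compares Table 2 with the protocol text, then bounds the number of patients affected.

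**Step 1. The Day 28 column.** Reading Table 2 row by row across its six visit columns, six items are marked at Day 28: medical history, concomitant medication, adverse events, ordinal scale, CT and chest X-ray.

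**Step 2. Table against text.**

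| Assessment | Marked in Table 2 | Text on follow-up or early discontinuation | Result |
|---|---|---|---|
| Inflammatory markers | Days 0, 3, 7, 10 | none | gap |
| Vital signs, including saturation | Screening, Days 0, 3, 7, 10 | saturation at each follow-up visit | conflict for saturation, gap for the rest |
| CBC | Screening, Days 0, 3, 7, 10 | none | gap |
| Metabolic panel | Screening, Days 0, 3, 7, 10 | at follow-up visits | conflict |
| Coagulation panel | Screening, Days 0, 3, 7, 10 | at follow-up visits | conflict |
| EKG | Days 0, 3, 7, 10 (later ones only if needed) | at screening and early discontinuation | conflict at both |
| Ordinal scale | Days 0, 3, 7, 10, 28 | phone-based at Day 28 | collected |
| CT, chest X-ray | Days 0, 28 | at discharge or 28 days, whichever is first | collected |

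Only the EKG text names the early discontinuation visit. The other conflicts concern follow-up visits. Day 28 is the only visit labelled follow-up, and the discontinuation visit inherits its content.

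**Step 3. Number affected.** The synopsis assumes 15% drop-out among 100 patients.

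- All drop-outs: 0.15 × 100 = 15.
- By arm, if drop-out is equal: 0.15 × 60 = 9 on HB-adMSCs and 0.15 × 40 = 6 on placebo.
- Patients who leave before the Day 10 visit and attend the exit visit: 15 × p × a, where p is the share of drop-outs leaving before Day 10 and a is the share of those who attend.

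The documents give neither p nor a. Each lies between 0 and 1, so the count lies between 0 and 15, reaching 15 only if p = a = 1.

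**Step 4. Use in the planned analyses.**

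- Leaves before infusion 4: outside the efficacy set, so no exit value enters a primary model. Inside the safety set if at least one infusion was given.
- Leaves after the Day 10 visit: the last scheduled marker and saturation measurements have already been reached.
- Stops infusions but keeps consent: stays on the full schedule and is not affected.

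**The case against.** The strongest objection is that the primary models need nothing from this visit. They use patients with all four infusions and scheduled measurements at Visits 2 to 5, so a patient leaving before infusion 4 is excluded whatever is measured at exit, and one leaving after Day 10 has passed the last marker visit. This stands. A reader might infer that the borrowed column deprives the primary analysis of data; as the plan is written, it does not.

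A second objection is that the protocol is not silent on exit safety tests, since the EKG and Risks texts call for several. This also stands, and it makes that part a contradiction rather than a clean omission. It does not settle which text sites follow. For the inflammatory markers and the CBC, no text contradicts the blank cells.

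Third, 15 should not be read as the number who would attend. Drop-out includes loss to follow-up and withdrawal of consent, attendance is required only if possible, and late withdrawals lose no scheduled marker. It is an upper bound. Nor do the documents support calling withdrawal the main source of missing primary data, since they do not quantify missingness by cause.

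Finally, the exit visit is not empty: the ordinal scale records the level of oxygen support, and imaging is kept.

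**Conclusion.** The point holds as a safety-data gap and an internal contradiction. Patients who leave before the Day 10 visit belong to the safety set but have no exit laboratory tests or vital signs scheduled in Table 2, while other protocol sections expect some of those tests. At most about 15 of 100 patients are affected. That bound assumes the protocol's 15% drop-out, withdrawal of all of them before Day 10, and full attendance at the exit visit; any relaxation lowers it.

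For efficacy the consequence is conditional. Exit markers and saturation would be useful only in an all-randomised or sensitivity analysis, not in the primary analysis under the four-infusion set. The change is worth making because the visit is already required and the missing values cannot be obtained afterwards.

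**What to change.** Add a separate early-discontinuation column to Table 2 and point the withdrawal section to it. It should contain the Day 10 assessments without the infusion, which covers vital signs with saturation, safety laboratory tests, inflammatory markers and the ordinal scale. It should keep the CT and chest X-ray from Day 28. Simply redirecting the visit to the existing Day 10 column would drop that imaging, which feeds two secondary endpoints.

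Reconcile the Electrocardiogram section with Table 2, and the Respiratory Risks, Hepatic Risks and Coagulation Cascade texts with the Day 28 column, so that each assessment has one stated schedule.

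State in the SAP how an exit value is assigned to a visit and which analyses use it. SAP 7.1.4.2 covers scheduled measurements only, and SAP 8.2 lists unscheduled laboratory data without tabulating them, so without a rule exit values could be collected and not analysed. If data collection has already ended, the SAP and the report should disclose the gap.

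The cost is protocol and SAP wording plus, for each withdrawing patient who attends, one set of blood tests, one set of vital signs and the other Day 10 assessments (physical examination, weight, PCR swab, exploratory markers) at a visit already required.
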